Abbreviations: 100DFU = 100-day follow-up; AE= adverse event; CNS = central nervous system; CR = complete response; CT = computed tomography; D/d = day; ECG = electrocardiogram; ECOG = Eastern Cooperative Oncology Group; EOT = End Of Treatment; FSH = follicle stimulating hormone; iRECIST = immunotherapy Response Evaluation Criteria in Solid Tumors; iCR = immune complete response; INR = international normalized ratio; iPR = immune partial response; IT = intratumoral; LTSFU = Long-Term Survival Follow-up; MRI = magnetic resonance imaging; N/A = not applicable; PD-L1 = programmed cell death protein ligand 1; PET = positron emission tomography; PR = partial response; PT = prothrombin time; PTFU = Post-treatment Follow-up; PTT = partial thromboplastin time; RECIST = Response Evaluation Criteria in Solid Tumors; Q3mo = every 3 months; Q3W = every 3 weeks; Q6W = every 6 weeks; SC = subcutaneous; SAE = serious adverse event; W = week; WOCBP = women of child bearing potential.

- a. End of Treatment assessments to be performed within 7 days following subject discontinuation from the last study treatment (either CMP-001 or nivolumab). Removal of a subject from CMP-001 treatment is defined as the time in which the Investigator decides to discontinue study treatment. If a subject has CMP-001 dosing withheld for more than 3 consecutive doses for any reason during the Q3W dosing period, resumption of treatment must be discussed with the Medical Monitor, otherwise, the subject will be discontinued from study treatment and will have all EOT assessments performed.
- b. The 100DFU is a safety follow-up visit that may be conducted at the study site or via phone. This visit should occur 100 days (+7) after the EOT.
- c. Post-treatment Follow-up (PTFU) will be conducted every 3 months (± 2 weeks) for all subjects who discontinue study treatment but have not met criteria for study discontinuation. These subjects should remain on study and receive disease assessments every 3 months, until discontinuation.
- d. Long-Term Survival Follow-up (LTSFU) will be conducted every 3 months (± 4 weeks) after the EOT visit or the last disease assessment date in PTFU and may occur via phone.

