## 7.7. Long-Term Survival Follow-up

Subjects who discontinue study treatment and PTFU will be contacted by the site according to the Schedule of Assessments (Table 1) for LTSFU, which will continue until death, withdrawal of consent, lost to follow-up, or End of Clinical Trial.

OS is a key endpoint of this study. Post-study follow-up is of critical importance and is essential to preserving subject safety and the integrity of the study. Subjects who discontinue study treatment must continue to be followed for collection of outcome and/or survival follow-up data as required until death or the conclusion of the study.

The Sponsor may request that survival data be collected on all treated subjects outside of the protocol-defined window (Schedule of Assessments, Table 1). At the time of this request,

each subject will be contacted to determine their survival status unless the subject has withdrawn consent for all contacts or is lost to follow-up.

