#### 9.6.3. Overall Survival

Overall survival will be calculated from the date of randomization to death from any cause (FDA-2018). Subjects who are alive at the time of analyses will be censored at the time of last study contact. Median OS will be calculated using the Kaplan-Meier method for each treatment arm OS will be analyzed using the same approach as PFS.

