Per Sponsor's decision, site activation and study enrollment were terminated early for any subjects who had not signed informed consent yet, and the trial has been changed to an exploratory Phase 2 study. Additionally, it has been decided that there would not be in-house blinding, hence the sponsor analysis and reporting team would be unblinded to the assignment of subject treatment. Consequently, the SAP will not necessarily be consistent with the protocol. In case of any discrepancies, this SAP will govern the analysis of data from this study.

II. Study Design

A. Design Overview

This is a randomized, open-label, active-control, exploratory Phase 2 study of first-line CMP-001 administered by intratumoral (IT) injection in combination with intravenous (IV) nivolumab versus nivolumab monotherapy in subjects with Stage III or IV unresectable or metastatic melanoma who have not been previously treated with a programmed cell death protein 1 (PD-1) blocking antibody for metastatic disease. Subjects will be randomized in a 1:1 manner to Arm A to receive CMP-001 IT in combination with nivolumab IV or Arm B to receive nivolumab monotherapy according to the Schedule of Assessments (Protocol Table 1) and Protocol Section 5.1.

During the randomization process, treatment groups will be stratified based on: TNM Stage American Joint Committee on Cancer (AJCC) Cancer Staging Manual Eight Edition (M0/M1a/M1b vs. M1c/M1d), and tumor PD-L1 expression (>=5% vs. <5%).

The primary endpoint of ORR per RECIST v1.1 as determined by BICR will be assessed approximately by two disease assessments after the enrollment of the last subject and the end of the study after a maximum duration of 2 years of study treatment. Subjects enrolled may remain in the study and continue to receive study treatment until a reason for treatment discontinuation is reached but no further subjects will be enrolled from 24Jun2022.

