- Start or stop date with missing both the month and day will not be imputed.
- Start date missing the day will be imputed as the 1st day of the month of the start date.
- Stop date missing the day will be imputed as the last date of the month of the stop date or the study first dose date, whichever comes earlier.

D. Multiple Study Centers

No adjustment for study center is planned. Data from all investigational sites will be pooled in the analyses.

E. Covariate Adjustment in Primary Analysis

No covariate adjustments are planned.

F. Sample Size Reassessment

Not applicable.

G. Ad-hoc Analysis

There will be an ad-hoc analysis planned with the trigger event being two disease assessments after the enrollment of the last subject. The ad-hoc analysis of the endpoints will follow the efficacy analysis methods described in Section 0 below as well as the safety analysis methods detailed in Section IX below for the exploratory Phase 2 study.

The following unblinded subject information, efficacy-related and safety-related data displays will be produced for the purpose of the ad-hoc analysis. Unless stated otherwise, these displays are summary tables that summarize data by treatment group:

- Subject information
 - Demographics
 - Baseline characteristics
 - Disposition

Regeneron Pharmaceuticals Inc. / Protocol: CMP-001-011 IQVIA Biotech (Confidential) Project # SZA58924

- Medical history
- Cancer history
- ECOG

Efficacy

- o ORR, DOR, TTR, PFS per RECIST v1.1 by BICR and Investigator
- o OS
- Selected subgroup analysis

Safety

- Study drug exposure: CMP-001 and nivolumab
- Prior and concomitant medications
- Prior and concomitant procedures
- o All TEAEs (SAE, AESI)
- Summary of clinical laboratory results
- Summary of ECG results

H. Test Sizes

Given Sponsor's decision to terminate the study enrollment early, any tested hypotheses will be exploratory in essence and tested against 2-sided alternatives, using procedures that provide an expected probability of Type I error (α) of 0.05.

I. Multiplicity

Provided that the study enrollment was terminated early per Sponsor's consideration and the trial has been changed to an exploratory Phase 2 study, the previous sequential gatekeeping strategy is not applicable here anymore, and there will be no control for multiplicity applied. Thus, any tests performed will simply be exploratory and interpreted as such.

J. Analysis Sets

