All events of RECIST v1.1 disease progression or death will be counted regardless of whether the event occurs while the subject is on study treatment or previously discontinued the study treatment. Subjects who do not experience disease progression or death as of the analysis cutoff date or final database lock will be censored at the date of the last adequate tumor assessment. Date of censoring for these subjects will be based on the last tumor assessment prior to missing the assessments. Censoring rules are summarized in Table 1. If a subject meets the criteria for more than one censoring rule, PFS will be censored at the earliest censoring date. Unless specified otherwise, the analysis methods described for DOR will be used for PFS. Additionally, the analysis of PFS based on RECIST v1.1 as determined by Investigator assessment will also be performed.

Overall Survival (OS). Overall survival will be calculated as the time from the date of randomization to the date of death due to any cause. Subjects who are alive or lost to follow-up as of the analysis cutoff date will be censored at the time of the last study contact date (i.e., date of last known alive). The last contact date will be derived as detailed in Table 2.

Based on these considerations, OS will be calculated as follows: OS (months) = (Death or Censoring Date – Date of Randomization + 1) / 30.4375

Regeneron Pharmaceuticals Inc. / Protocol: CMP-001-011 IQVIA Biotech (Confidential) Project # SZA58924

OS will be analyzed using the Kaplan-Meier method by treatment arm of the ITT Analysis Set. A Kaplan-Meier plot of OS will be generated for each treatment arm. The analysis methods described for DOR will be used for OS, unless specified otherwise.

Disease Control Rate (DCR). The confirmed disease control rate is defined as the proportion of subjects in each treatment arm in the analysis set who have a confirmed best response of CR, PR, or stable disease (SD) lasting at least 4 months. Per RECIST v1.1, CR or PR must be confirmed by a confirmatory assessment performed at least 4 weeks after the initial response. In the case of SD, measurements must have met the SD criteria at least once after study entry at a minimum interval of 6 weeks. Overall response assessment evaluated after subsequent new anti-cancer therapy will not be considered for DCR calculation.

DCR will be analyzed in a similar manner as ORR. Specifically, DCR and the associated 95% Clopper-Pearson CIs will be summarized.

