Regeneron Pharmaceuticals Inc. / Protocol: CMP-001-011 IQVIA Biotech (Confidential) Project # SZA58924

iUPD per iRECIST, continued study treatment with subsequent disease assessments but no confirmed PD (i.e., iCPD not assigned) or death as of data cutoff date and subject not received new anticancer therapy or received it after the data cutoff date	Censored	Date of the last tumor assessment as of data cutoff date	Alive without Documented iCPD	X
iUPD per iRECIST, continued study treatment, but started a new anti- cancer therapy before data cutoff date without evidence of iCPD or death	Censored	Date of the last tumor assessment prior to new anti- cancer therapy	Subsequent Anti- cancer Therapy without Documented iCPD	X
iCPD per iRECIST or death after new anticancer therapy and the new anticancer started before data cutoff date	Censored	Date of last disease assessment prior to new anticancer therapy	iCPD or Death after Subsequent Anti-cancer Therapy	X
iCPD per iRECIST or death after new anticancer therapy and the new anticancer started after data cutoff date	Censored	Date of last disease assessment on/before data cutoff date	iCPD or Death after Subsequent Anti-cancer Therapy	X
iUPD per iRECIST, continued study treatment, iCPD or death immediately following two or more consecutive disease assessments since the last adequate disease assessment	Censored	Date of last adequate tumor assessment prior to the first missed assessment	iCPD or Death after Missing >= 2 Consecutive Disease Assessments	X
Discontinuation from study before iCPD per iRECIST and death	Censored	Date of last adequate disease assessment	Discontinued from Study without Documented iCPD or Death	X

Situation	Outcome	Date	Event Description/ Censoring Reason	os
Death on/before data cutoff date	Event	Date of death	Death	X

Alive with study completed before data cutoff date	Censored	Study completion date	Alive on or before study completion date	X
Alive or death after data cutoff date with study continuing on/till after data cutoff date	Censored	Data cutoff date	Alive on or before data cutoff date	X
Lost to follow-up prior to data cutoff date	Censored	Last known alive date	Discontinued from study	X
Discontinued study without death and not lost to follow-up on/prior to data cutoff date	Censored	Date of study discontinuation	Discontinued from study	X

Table 2: Last Known Alive Date for the Overall Survival

Source Data	Conditions

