Last contact date/last date patient known to be alive from Long-Term Follow-Up eCRF 100-Day Follow-Up eCRF	Use if patient status is reported to be alive. Do not use if patient status is not reported unknown
End of study	Not lost to follow up
Start/end dates from drug administration record	Non-missing dose. Doses of 0 are allowed
Dosing prophylaxis eCRF	Prophylaxis given marked as yes
End of treatment date(s) from the End of Treatment eCRFs	No condition
Tumor assessment (RECIST v1.1 or iRECIST) date	Evaluation is marked as done
Laboratory/PK collection dates	Sample collection marked as done
Vital signs date	At least 1 non-missing parameter value
Physical examination	Evaluation performed marked as yes
12-Lead ECG	Evaluation performed marked as yes
ECOG performance status date	Non-missing ECOG performance status
Start/end dates of adverse events	Non-missing verbatim term
Start/end dates of concomitant medications and procedures	Non-missing verbatim term

B. Primary Efficacy Analysis

Primary Efficacy Endpoint. The primary efficacy endpoint for the exploratory Phase 2 study is the confirmed ORR based on RECIST v1.1 as determined by BICR. ORR and the 95% exact CIs will be calculated using the Clopper-Pearson method for each of the 2 treatment arms in the ITT Analysis Set.

Regeneron Pharmaceuticals Inc. / Protocol: CMP-001-011 IQVIA Biotech (Confidential) Project # SZA58924

Given Sponsor's decision to terminate the study enrollment early, the previous sample size calculated to achieve the power and effect size desired at the confidence level specified will not be reached. Hence, the analysis will simply be exploratory and interpreted as such.

C. Secondary Efficacy Analyses

The secondary efficacy endpoints include DOR, PFS, OS, DCR, treatment effect in non-injected target lesions based on the RECIST v1.1 by Investigator assessment, iORR, iDOR, and iPFS. Post-progression disease assessments of tumor response based on iRECIST evaluated by Investigator assessment will be summarized in a similar way to the RECIST v1.1 assessment, and will include the calculation of iORR, iDOR, and iPFS by treatment arm using the ITT Analysis Set as described in the previous sections.

iORR: As assessed by Investigator assessment according to iRECIST for the ITT Analysis Set in each of the treatment arm, iORR will be summarized and analyzed in a similar fashion to that of the ORR per RECIST v1.1.

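### SAP VIII.A: the OS censoring row for subjects still on study uses a different date from the OS text, and the PFS row for never-scanned subjects does not exclude deaths

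*SAP*

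**What the plan says.** **Overall survival.** The OS paragraph of SAP VIII.A says that subjects living or lost to follow-up at the analysis cutoff "will be censored at the time of the last study contact date (i.e., date of last known alive", and refers to Table 2 for deriving that date. Protocol 9.6.3 has the same rule: "Subjects who are alive at the time of analyses will be censored at the time of last study contact". The OS rows after SAP Table 1 divide censored subjects into four cases. Three of them use the study completion date, the last-known-alive date (lost to follow-up) and the study discontinuation date. The fourth, "Alive or death after data cutoff date with study continuing on/till after data cutoff date", uses the data cutoff date.

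On precedence, SAP I.B states: "In case of any discrepancies, this SAP will govern the analysis of data from this study". This places the SAP above the protocol. It does not rank the SAP's text against its own tables.

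**Progression-free survival.** SAP VIII.A counts PFS from randomization to BICR progression or death from any cause, and applies default censoring only to subjects with neither. In Table 1:
- One row makes a death without documented progression and without new anticancer therapy an event on the date of death. It requires no earlier scan.
- Another row, for PFS only, covers subjects who have no disease assessment after baseline and censors them at first dose. It does not mention death.
- The next two rows both state that neither progression nor death has occurred.

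The only written tie-break says that a subject who meets several censoring rules takes the earliest of their dates.

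**The concern.** Both rows can put the wrong input into a Kaplan-Meier estimate if they are programmed as written.

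For OS, two programmers working from the same section could give one subject two censoring dates. The cutoff date credits the subject with survival time that no contact supports. This matters mainly at the early look described in SAP VI.G, which lists OS among its outputs and falls while subjects may still be on study: "There will be an ad-hoc analysis planned with the trigger event being two disease assessments after the enrollment of the last subject".

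For PFS, a literal reading of the row turns an early death, the least favourable outcome, into a censoring at the start of follow-up. The same subject would then be handled inconsistently elsewhere in the SAP. A death from progression before any scan is classed as PD for best overall response. The no-assessment row does not apply to iPFS, so the same death would be an iPFS event.

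The outputs at stake are the curves, the medians, the 6- and 12-month rates and the tables of censoring reasons. The analysis team is unblinded (SAP I.B), so the rule is better settled before anyone sees which choice affects whom.

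**Working it through.** The plan states no figure that depends on these rules, so there is nothing of its own to reproduce. The check is a comparison of the rules, with small calculations to show direction and size.

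**OS, case by case for a subject still on study**

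| Subject | OS text | OS row | Agree? |
|---|---|---|---|
| Known alive after the cutoff | Alive at cutoff, so cutoff once follow-up is truncated there | Cutoff | Yes |
| Died after the cutoff | Same | Cutoff | Yes |
| Living, last contact before the cutoff | Last contact | Cutoff | No |

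The other three OS censoring rows are broadly compatible with the text. The lost-to-follow-up row uses the last-known-alive date directly. Table 2 accepts the end-of-study date under the condition "Not lost to follow up", which fits the completion and discontinuation rows.

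*Direction.* Each Kaplan-Meier factor is 1 − d/n, with d deaths among n at risk. With recorded deaths held fixed, later censoring can only increase n or leave it unchanged. Every factor is therefore at least as large, and the curve is the same or higher.

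*Illustration on assumed data:* deaths at 4, 8 and 11 months, cutoff at 12 months, three living subjects last contacted at 9 months, the other living subjects at 11.9 months. The curve after the 11-month death is:
- n = 9, last contact: 8/9 × 7/8 × 3/4 = 0.583. Cutoff: 8/9 × 7/8 × 6/7 = 0.667.
- n = 11, last contact: 10/11 × 9/10 × 5/6 = 0.682. Cutoff: 10/11 × 9/10 × 8/9 = 0.727.

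*Gap between the two dates.* Protocol Table 1, note d: "Long-Term Survival Follow-up (LTSFU) will be conducted every 3 months (± 4 weeks". By that schedule the last contact can precede the cutoff by about 3 months, or 3 + 28/30.4375 = 3.92 months if the next contact is 4 weeks late. This is a nominal figure for that stage only and is not a bound. The documents give no contact dates or deaths, so the size of the effect on the curve cannot be derived.

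**PFS, one death before any scan and without new anticancer therapy**

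1. The first scan is due at W10D1, which is Day 1 + 9 × 7 = Day 64 (−7 days). A death before then would ordinarily have no post-baseline scan.
2. Death-event row: all conditions met, event on the date of death.
3. No-assessment row: condition met, censored at first dose.
4. Tie-break: it orders censoring rules among themselves and does not choose between an event and a censoring.

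Arm sizes are 9 (Arm A) and 11 (Arm B), from SAP II.C. If this death is the arm's first event:
- Arm A: 8/9 = 0.889 if counted, 1.0 until the next event if censored.
- Arm B: 10/11 = 0.909 if counted, 1.0 until the next event if censored.

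*Effect at 6 months, on assumed data* (one such death, then 2 or 4 progressions by 6 months, all others followed beyond 6 months):

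| Arm | Progressions | Death counted | Death censored |
|---|---|---|---|
| A | 2 | 6/9 = 66.7% | 6/8 = 75.0% |
| A | 4 | 4/9 = 44.4% | 4/8 = 50.0% |
| B | 2 | 8/11 = 72.7% | 8/10 = 80.0% |
| B | 4 | 6/11 = 54.5% | 6/10 = 60.0% |

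One such subject moves the 6-month rate by about 5 to 8 percentage points in these examples.

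**The case against.** **On OS,** the row can be read as covering subjects whose status after the cutoff is known. They were alive at the cutoff, so row and text agree. That is correct for those subjects and narrows the conflict. It does not remove it: on that reading, a continuing subject last contacted before the cutoff has not completed, discontinued or been lost, and so fits no OS row. The mismatch with the protocol adds no independent weight, because the SAP governs. The conflict that matters lies inside the SAP.

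**On PFS,** the text largely settles the intent. The definition includes death from any cause. Default censoring is limited to subjects with neither event. The same paragraph says that events count whether or not the subject is still on treatment, and presents Table 1 as a summary. Rows meant to censor a death name it. All of this stands. It shows that the row is incomplete, not that the ambiguity is absent, because a program built from Table 1 would still meet two matching rows. Exclusion criterion 23 (life expectancy under 3 months) makes such deaths less likely but does not rule them out.

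**A stronger reading** would add the row on missed consecutive assessments: a reader might infer that a never-scanned subject who dies late is censored at the baseline scan, giving zero or negative PFS time. The documents do not support this. Nowhere do they call a baseline scan an adequate assessment for that row, and the reason attached to the no-assessment row, that no adequate assessment exists, points the other way.

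**Conclusion.** Both inconsistencies are in the text, and both are minor.

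- **OS:** the conflict is confined to one row and to living, continuing subjects last contacted before the cutoff. With recorded deaths fixed, the row's rule can only leave the curve unchanged or raise it. The size cannot be determined from the documents.
- **PFS:** the no-assessment row is inconsistent with the SAP's own definition. A reader might infer that the SAP intends to censor early deaths, but the definition and text show the opposite. The drop lost from the curve would be 1/9 = 11.1 points (Arm A) or 1/11 = 9.1 points (Arm B), if the row were applied to one such death and that death were the arm's first event.

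The 6-month PFS figures and the OS curves rest on assumed event times and are not trial data. PFS and OS are exploratory secondary endpoints in 20 subjects, no document reports a subject of either kind, and the primary endpoint, ORR, does not use these rules.

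**What to change.** 1. **OS row.** Replace the data cutoff date with the earlier of the data cutoff date and the last-known-alive date. State that any later contact, or a death after the cutoff, shows the subject alive at the cutoff, so that such subjects remain censored at the cutoff. Restricting Table 2 to contacts before the cutoff would wrongly move them back to an earlier visit.
2. **PFS row.** Limit the row to subjects with neither a post-baseline disease assessment nor a death, and state that the death-event row takes precedence over it.
3. **Optional.** Protocol 7.7 already allows a survival-status check: "The Sponsor may request that survival data be collected on all treated subjects outside of the protocol-defined window". Confirming status on or after the cutoff would bring the two OS rules into agreement for every living subject reached.

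The first two changes cost a few lines of SAP wording and minor reprogramming, and need no new data. The third means one extra contact for subjects not otherwise seen around the cutoff.

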## 4.5. Treatment Discontinuation

Treatment discontinuation is defined as any subject who stops receiving study treatment and does not restart within 12 weeks. Subjects who permanently discontinue (for >12 weeks) CMP-001 or nivolumab may not be re-treated with the discontinued study treatment in this study. When nivolumab is permanently discontinued due to an immune related AE, CMP-001 must also be permanently discontinued.

Treatment with study treatment should continue until one of the following occurs:

- Unacceptable AE that precludes further study treatment
- 2 years of study treatment
- PD per RECIST v1.1; continuation of treatment through suspected pseudoprogression is permitted at the Investigator's discretion until confirmed PD per iRECIST
- Upon request of the Sponsor or regulatory agency
- Clinical disease progression in the opinion of the Investigator
- If medically necessary in the opinion of the Investigator
- Subject withdraws consent for study treatment
- Subject has received study treatment for 2 years
- Subject becomes pregnant or begins breastfeeding

- Subject is lost to follow-up
- Death
- End of Clinical Trial

If a subject achieves and maintains a confirmed CR or iCR by Investigator assessment, IT or SC injections of CMP-001 or the combination of CMP-001 and nivolumab may be discontinued at the Investigator's discretion once the subject meets both of the following criteria:

- Subject has been treated for at least 48 weeks (the maximum duration of study treatment is 2 years)
- Subject has received at least 3 doses of assigned treatment beyond the date of the initial CR/iCR

Subjects with PD per RECIST v1.1 as determined by Investigator assessment should remain on treatment and have a follow-up scan performed at least 4 weeks after the initial date of PD to confirm progression per RECIST v1.1 by BICR.

Subjects who discontinue study treatment should complete an EOT visit and 100-day safety follow-up contact, which should occur 100 days (+7) after the EOT or until an alternative cancer treatment is initiated, whichever occurs first (Table 1). Subjects who discontinue study treatment for reasons other than disease progression (either per RECIST v1.1 or iRECIST by Investigator assessment) should remain on study for PTFU (Section 7.6) and receive disease assessments according to the Schedule of Assessments (Table 1).

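### SAP Table 2 accepts the End-of-Treatment date as proof of life without excluding subjects lost to follow-up, so their OS can be censored later than the last real contact

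*SAP*

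**What the plan says.** The OS paragraph of SAP VIII.A states that "Subjects who are alive or lost to follow-up as of the analysis cutoff date will be censored" at the last contact date, and that "The last contact date will be derived as detailed in Table 2". In the OS event and censoring rows printed just before Table 2, the row "Lost to follow-up prior to data cutoff date" is the only one that censors at the last known alive date. The other censoring rows use study completion, data cutoff or study discontinuation.

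Table 2 lists the acceptable sources. Three rows matter here:

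- The End-of-study date counts only if the subject is "Not lost to follow up".
- "End of treatment date(s) from the End of Treatment eCRFs" counts with no restriction.
- Drug administration dates count under "Non-missing dose. Doses of 0 are allowed".

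Loss to follow-up is a reason for stopping treatment in Protocol 4.5 and in the treatment disposition list of SAP VII.B. On timing, Protocol 4.5 says "Treatment discontinuation is defined as any subject who stops receiving study treatment and does not restart within 12 weeks". Note a to Protocol Table 1 says "Removal of a subject from CMP-001 treatment is defined as the time in which the Investigator decides to discontinue study treatment". The same note places EOT assessments within 7 days of discontinuation.

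**The concern.** The restriction on the End-of-study row exists for a clear reason: for a subject who has disappeared, the date on a closing form need not be a date on which anyone knew the subject was alive. The EOT form can be closed for the same reason, yet its row carries no such restriction. The gap affects exactly the subjects for whom Table 2 sets the OS censoring date.

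If the EOT date is entered after the last real contact, the subject stays in the OS risk set without evidence of survival. A death among the other subjects during that time is then divided by too large a number at risk.

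There is a second route. SAP VI.C imputes a partial death date no earlier than the day after the last known alive (or last contact) date. For a subject with a partial death date, a late EOT date could therefore move an OS event as well.

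**Working it through.** The plan states no figure for this rule, so there is none to reproduce. The check traces the rule and then sizes it on assumed data.

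**Inputs**

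- Arm sizes 9 (Arm A) and 11 (Arm B): SAP II.C.
- Days per month 30.4375: OS formula, SAP VIII.A.
- 12 weeks = 84 days: Protocol 4.5. 7 days: Protocol Table 1, note a. 21 days: exposure formula, SAP IX.A.
- Not given: the meaning of the EOT eCRF date, the number lost to follow-up, and the length of any gap.

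**Step 1. When the EOT date decides.** Using the latest qualifying date is implied by the title of Table 2 but not written. On that reading, the EOT date matters only when it is later than every other accepted date. Protocol Table 1 schedules physical examination, vital signs, ECOG status, ECG and laboratory tests at EOT. Each has its own Table 2 row, conditional on having been done or having a value. An attended EOT visit is therefore normally captured already, and the unrestricted row adds something mainly when no such contact is documented.

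**Step 2. Can the date run past the last dose?** The exposure formula in SAP IX.A takes the earlier of last dose plus 21 days and the discontinuation or completion date. That cap has a purpose only if the discontinuation date can fall more than 21 days after the last dose.

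**Step 3. Shift in one censoring time.** Months = days / 30.4375, for assumed gaps:

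- 21 / 30.4375 = 0.69
- 84 / 30.4375 = 2.76
- (84 + 7) / 30.4375 = 91 / 30.4375 = 2.99

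**Step 4. Effect on Kaplan-Meier OS.** Assume *k* lost subjects last seen at month 4, EOT dates 84 days later (month 6.76), and one death at month 5. Six-month OS is (*n* − *k* − 1)/(*n* − *k*) when censoring is at last contact, and (*n* − 1)/*n* when it is at the EOT date.

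| Arm | Lost | Last contact | EOT date | Difference (points) |
|---|---|---|---|---|
| A, n=9 | 1 | 7/8 = 87.5% | 8/9 = 88.9% | 1.4 |
| A, n=9 | 2 | 6/7 = 85.7% | 8/9 = 88.9% | 3.2 |
| A, n=9 | 3 | 5/6 = 83.3% | 8/9 = 88.9% | 5.6 |
| B, n=11 | 1 | 9/10 = 90.0% | 10/11 = 90.9% | 0.9 |
| B, n=11 | 2 | 8/9 = 88.9% | 10/11 = 90.9% | 2.0 |
| B, n=11 | 3 | 7/8 = 87.5% | 10/11 = 90.9% | 3.4 |

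With no death between the two dates, the difference in every row is zero.

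**Step 5. Scale.** The Greenwood standard error for a single step is √(S(1 − S)/n). At 8/9 with n=9 it is √((8/9)(1/9)/9) = 10.5 points. At 10/11 with n=11 it is √((10/11)(1/11)/11) = 8.7 points.

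**The case against.** A reader might infer that lost subjects *are* counted alive to an administrative date, by up to 12 weeks, and that Kaplan-Meier OS is biased upward as a result. The documents do not support that.

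- **The EOT date is undefined.** It may be the last dose or an attended visit, and then there is no error. The eCRF and its completion guide, which would settle this, are not among the documents.
- **Twelve weeks is not a bound.** Protocol 4.5 does not say that the EOT date is entered at week 12. Note a covers CMP-001 only, which Arm B does not receive. Protocol 5.1.4 allows some delays beyond 12 weeks. The 84 days are an assumption.
- **Zero-dose records are not shown to be unattended visits.** Protocol 5.1.1 says dosing visits are delayed rather than skipped, and a dose withheld at an attended visit is proof of life.
- **The route is narrow.** The 100-day contact and the 3-monthly survival follow-up continue after treatment, and any later contact overrides the EOT date. No lost subjects are reported.
- **Death imputation concerns other subjects.** It applies to those known to have died with a partial date, not to those censored as lost.

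All of this stands as a limit on certainty and size. It does not explain why one closing-form date is barred for lost subjects and the other is not. The undefined date is itself a reason to restrict the row.

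**Conclusion.** The point holds as a conditional one. Table 2 treats two closing-form dates inconsistently, and a subject lost on treatment *can* be censored for OS later than the last real contact. This requires an EOT date that is administrative and later than every other qualifying Table 2 date. The Kaplan-Meier estimate then changes only if a death falls in the gap.

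In the assumed examples the change is 0.9 to 1.4 points with one lost subject and at most 5.6 points with three. The one-subject figures are small beside standard errors of about 9 to 10 points. The shift of an imputed partial death date is possible under the same condition on the EOT date, but no case of it is shown. The zero-dose row is a minor adjunct.

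Severity is low: OS is a secondary, descriptive endpoint in a 20-subject exploratory study, and the real effect may be nil.

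**What to change.** In the EOT row of SAP Table 2, replace the absence of a condition with: *Use only if the EOT visit or contact took place and the reason for ending treatment is neither lost to follow-up nor death.* This mirrors the End-of-study row. As a minor addition, accept zero-dose records only when the visit was attended.

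The cost is two table cells and a few lines of code. Little genuine follow-up is lost, because an attended EOT or dosing visit normally leaves a vital-signs date, or another conditioned date, that Table 2 already accepts. The downside is slightly earlier censoring for some lost subjects. If no subject was lost, OS censoring does not change.
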